***Blueberries, Gut Microbiota, and Metabolites in
Depressed Older Adults - A Pilot Study aka Berries,
Bugs, and the Blues***

Study Protocol
IRB# Pro00068528
NTC# 05817383

CHAPTER 1. INTRODUCTION

Emerging evidence indicates the trillions of microbes residing in the gut play an integral role a mediating physiological pathways of depression (e.g., neuro-inflammation and neurotransmitters). Given that diet is a potent modulator of the gut microbiota, the long-term goal of this project is to identify nutrients that interact with the gut microbiota processes/pathways relevant to depression. Our preliminary data suggests that intake of dietary fiber and anthocyanins (class of flavonoids found in berries) are associated with reductions in depressive symptoms. Coincidentally, fiber and anthocyanins are metabolized by microbes, and influence the gut microbial communities and metabolites relevant to depression (i.e., short chain fatty acids, SCFA). However, it is unknown if the nutrient-gut microbiota-interaction is the mechanism underlying the beneficial association between fiber and anthocyanin intake with depression. Our objective is to determine if consuming a whole-food source of dietary fiber and anthocyanins (via freeze-dried blueberry powder) modulates the gut microbiota, SCFA, and improves depressive symptoms. This study is an ancillary project to a currently funded randomized, placebo-controlled 12-week intervention in older, sedentary adults with depressive symptoms (**IRB# Pro00064749**). This specific project proposes distinct aims to the trial by gathering preliminary data on the synergistic impact of dietary fiber and anthocyanins on the gut-microbiota, gut-derived metabolites, and depressive symptoms in older adults. This study will provide evidence on the utility of fiber- and anthocyanin-rich agricultural foods as a new therapeutic opportunity to improve human health by modulating the gut microbiota and relevant metabolites.

CHAPTER 2. BACKGROUND

2.1 Urgency to Address Age-related Depression: Between 8-16% of community-dwelling older adults have clinically relevant depressive symptoms,¹ which is marked by severe feelings that significantly impair daily function.² As a result, individuals with depressive symptoms/depression have increased risk of disability, chronic depression, and suicidal ideation.³⁻⁷ Older adults prefer non-pharmacological approaches,⁸ yet underutilize psychotherapy (an effective treatment regimen for depression)⁹ due to its high cost and inaccessibility, which prevents many older adults from obtaining adequate care⁸ and underscores the need for novel therapeutic strategies.

2.2 Diet, the Gut, and Depression: The gut microbiota directly impact several pathophysiological pathways of depression (e.g., neuro-inflammation).¹⁰⁻³¹ Dietary modification of the gut microbiota³⁰⁻³⁴ offers an accessible, low-cost approach to help improve depression in the millions of older adults with depressive symptoms. Epidemiological studies have linked intake of dietary fiber (i.e., fiber found naturally in foods) or anthocyanins (a class of flavonoids with antioxidant properties) with the prevention of depression.³⁵⁻³⁹ Our preliminary data from a prospective cohort study also suggests that increasing dietary fiber and anthocyanin intake were associated with reduced depressive symptom severity in older adults (**Table 1**). Human studies increasing intake of dietary fiber and anthocyanins are needed to confirm their potential to improve depression and elucidate the role of the gut microbiota as an underlying mechanism.

Dietary Component	Beta*(SE)	P-value
Anthocyanins (per 60 mg)	-1.9(0.6)	0.01
Fiber (per 60 mg)	-1.2(0.4)	0.01

Adjusted for age, sex, and calorie intake. CES-D, center for epidemiological studies depression scale; SE, standard error;

2.3 Fiber and Anthocyanins to Modulate the Gut: Dietary fiber⁴⁰⁻⁴³ and anthocyanins^{32,44-51} interact with the gut microbiota, which may contribute to their protective associations with depression.⁵² Both nutrients are metabolized by gut microbes, which helps shape the number and types of microbes present in the gut, as well as the gut-derived metabolites.⁵² Certain types of dietary fiber are metabolized by some microbes to directly produce short chain fatty acids (SCFA). Increased production of SCFA may improve depressive symptoms given their ability to reduce neuro-inflammation and increase proteins essential for neuron formation.³⁰ Research suggests that anthocyanins promote the enrichment of SCFA-producing microbes to indirectly increase production of SCFA.⁵³⁻⁵⁵ We hypothesize intake of dietary fiber and anthocyanins synergistically increase gut-derived SCFA and exert a protective effect on depression (**Figure 1**).

[figure not shown]

Figure 1. Conceptual Model. We hypothesize the dietary fiber in freeze-dried blueberry powder will be metabolized by gut microbes to directly increase SCFA, and the anthocyanins in freeze-dried blueberry powder will increase the prevalence of gut microbes that metabolize fiber into SCFA to indirectly increase SCFA. The SCFA, which have been associated with reduced neuro-inflammation and increase production of factors needed for neuron formation, will reduce depressive symptoms. SCFA, short chain fatty acids;

CHAPTER 3: RESEARCH DESIGN

[figure not shown]
3.1 Study Objectives and Aims

Our objective is to gather preliminary evidence on the synergistic impact of dietary fiber and anthocyanin intake on the gut microbiota-related pathways/processes relevant to depression utilizing a whole-food approach. We propose an ancillary study to a currently funded (**IRB Approval Pro00064749; Co-PI [name]**) randomized, double-blind, placebo-controlled intervention in older adults (≥ 65 y) with depressive symptoms (see §3.2 for details on the ancillary study design; **Figure 2**). The aims of this ancillary project are:

Aim 1: Determine the impact of daily dietary fiber and anthocyanin (via freeze-dried blueberry powder) intake on microbes that produce gut-derived SCFA in older adults with depressive symptoms by performing a randomized, placebo-controlled, double-blind trial.

Aim 2: Determine the effect of daily dietary fiber and anthocyanin intake on fecal SCFA in older adults with depressive symptoms, participating in the clinical trial.

Aim 3: Determine the effect of daily dietary fiber and anthocyanin intake on depressive symptom severity in older adults with depressive symptoms, participating in the clinical trial.

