3.6 Study Intervention Products

In the parent study, participants will be randomized to consume either 48 g of freeze-dried blueberry powder (**equivalent to ~2 cups of fresh, whole blueberries**) or 48 g of placebo powder each day for this 12 week intervention. A single batch of freeze-dried blueberry powder and a single batch of placebo powder will be provided by the US Blueberry Council. A 48 g dose of the freeze-dried blueberry powder provides ~8 g of dietary fiber and ~600 mg of anthocyanins. The powder will be packaged into individualized packets (24 g/packet), and individuals will be instructed to consume 1 packet in the morning and 1 in the afternoon (i.e., 48 g/day). The placebo powder is a nutritionally matched powder (primarily consisting of maltodextrin, fructose, and dextrose) that is devoid of dietary fiber and anthocyanins. *Given that microbes are ubiquitous (even on blueberries⁶⁰), we will evaluate the microbial content of the freeze-dried blueberry and placebo powder. We will preliminarily explore if microbes on foods are similar to the microbes that reside and proliferate in the gut.* Prior to the intervention, similar methods will be used as described for the fecal microbiota techniques in §3.5

To allow for blinding, the placebo powder will be labeled with either a letter or number that is different from the intervention powder. This is a double-blind intervention, so neither the participants nor the study staff will know which powder is the placebo and/or which is the blueberry powder. See §3.6 for further information on dietary intervention.

CHAPTER 4 RECRUITMENT AND DATA COLLECTION

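### Section 3.1 and Chapter 1 promise evidence on fiber–anthocyanin synergy, but the two-arm contrast estimates only the powder's total effect and cannot separate synergy from additivity or a single-nutrient effect

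*Combined protocol and SAP*

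**What the plan says.** Synergy appears in three places in the protocol.

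- Section 3.1 gives the objective: to "gather preliminary evidence on the synergistic impact of dietary fiber and anthocyanin intake".
- Chapter 1 describes the project's distinct contribution as "gathering preliminary data on the synergistic impact of dietary fiber and anthocyanins on the gut-microbiota", together with metabolites and symptoms.
- Section 2.3 states: "We hypothesize intake of dietary fiber and anthocyanins synergistically increase gut-derived SCFA and exert a protective effect on depression". The Figure 1 legend adds a mechanism: fiber is fermented to SCFA directly, and anthocyanins enrich the microbes that do the fermenting.

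The design is in sections 3.2, 3.6 and 5.3. In section 3.6, "participants will be randomized to consume either 48 g of freeze-dried blueberry powder" or the same weight of placebo. On content, "A 48 g dose of the freeze-dried blueberry powder provides ~8 g of dietary fiber and ~600 mg of anthocyanins", while the placebo is "devoid of dietary fiber and anthocyanins". No arm receives one nutrient without the other, and the powder dose does not vary.

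Section 6.2 compares blueberry with placebo throughout: a per-feature linear model by treatment for Aim 1, a two-sample t-test on change in butyrate for Aim 2, and the same method on CES-D change for Aim 3. It specifies no interaction term and no analysis that separates the components.

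Chapter 1 also states a second objective, without reference to synergy: whether eating a whole food that supplies both nutrients changes the microbiota, SCFA and depressive symptoms.

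**The concern.** Synergy in the usual sense means that the joint effect exceeds the sum of the separate effects. The Figure 1 mechanism, in which one nutrient changes what the gut does with the other, reads as a claim of that kind. To estimate it, one must know what each nutrient does alone, and a both-versus-neither allocation does not supply that.

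What is at stake is the conclusion that may be drawn. Section 8.6 ties the planning of later trials to findings that confirm the hypotheses, and synergy is one of the stated hypotheses. A positive blueberry-versus-placebo difference, reported against the objective in section 3.1, would be read as preliminary support for synergy when it is equally compatible with no synergy. Calling the evidence preliminary does not help, because the limit is identifiability and not precision.

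**Working it through.** The plan gives no interaction effect size, power or sample size, so there is no figure to reproduce. The check is one of estimability.

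**Inputs.** Two arms (sections 3.2, 3.6, 5.3): blueberry has fiber = 1 and anthocyanin = 1; placebo has fiber = 0 and anthocyanin = 0. Section 6.2 gives 20 per group, an SD of CES-D change of 3.5, a CES-D target of 2 points, an SD of butyrate change of 0.32% and a butyrate target of 0.3%.

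**Step 1: the model.** With x for fiber and z for anthocyanin, E[Y] = b0 + F·x + A·z + FA·x·z.

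- Placebo mean: b0
- Blueberry mean: b0 + F + A + FA
- Difference: T = F + A + FA

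There are two cell means and four parameters.

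**Step 2: is FA estimable?** The distinct design rows are (1,0,0,0) and (1,1,1,1), so the rank is 2 of 4. Any linear combination of these rows puts equal weight on F, A and FA, so (0,0,0,1) cannot be formed. The rank is the same at 20 per arm and at 100,000 per arm.

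**Step 3: what a positive result would fit.** Take T = −2 CES-D points (negative is benefit).

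| F | A | FA | T | Reading |
|---|---|---|---|---|
| −2 | 0 | 0 | −2 | one nutrient only |
| −1 | −1 | 0 | −2 | additive |
| 0 | 0 | −2 | −2 | pure synergy |
| −2 | −2 | +2 | −2 | antagonism |

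In no row is either nutrient harmful, so assuming the direction of the separate effects does not choose among them.

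**Step 4: what a null would fit.** Score effects so that benefit is positive. If F ≥ 0 and A ≥ 0, then FA = T − F − A ≤ T, so an upper confidence limit for T is also an upper limit for FA. At 20 per arm the 95% half-width for T is t(38 df) × SD × √(2/20):

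- CES-D: 2.024 × 3.5 × 0.316 = 2.24 points
- Butyrate: 2.024 × 0.32 × 0.316 = 0.20%

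An observed CES-D difference of exactly zero would thus cap synergy at about 2.2 points, which is above the 2-point target. For butyrate the cap would be about 0.2%, below the 0.3% target. Both caps depend on the sign assumption.

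**Step 5: would a factorial be a realistic alternative?** A 2×2 layout has rank 4 of 4, so FA becomes estimable, with SE = SD × √(4/n per cell). The interaction sizes below are assumptions, because the documents give none; tests are two-sided at 0.05.

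- CES-D, same 40 participants (10 per cell): SE = 3.5 × √0.4 = 2.21 points. Power for a 2-point interaction is about 15%.
- CES-D, 80% power: n per cell = 4 × (3.5 × 2.802 / 2)², rounded up to 97 (388 in total). For 1 point it is 385 per cell (1,540 in total).
- Butyrate, 10 per cell: power for a 0.3% interaction is about 32%. For 80% power, 4 × (0.32 × 2.802 / 0.3)², rounded up to 36 per cell (144 in total).

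**The case against.** **The plan already has an answerable objective, and nothing operational rests on synergy.** This stands. The second objective in Chapter 1, Aims 1–3, the endpoints and all of section 6.2 concern the joint effect. The objective in section 3.1 also goes on to mention a whole-food approach. Section 8.6 describes what confirmation would show in terms of a dietary intervention, not synergy. The mismatch is therefore confined to three statements, and no planned analysis would change.

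**Synergistic may have been meant loosely, as combined.** This is possible, since the documents do not define the term. But the Figure 1 mechanism supports the stricter reading, and if the loose sense was meant, the text should say combined.

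**Diet records vary, so intake of each nutrient is not fixed within arms.** This is true but of little help. The intake data are self-reported and not randomised, the washout restricts intake before baseline, and no interaction analysis on them is planned.

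**A reader might infer that the trial carries no information on synergy and that a null could not count against it.** The documents do not support that. Section 2.3 expects both nutrients to raise SCFA, one directly and one indirectly. Under those signs a precise null bounds positive synergy from above, as in step 4. What holds is narrower: synergy is not point-identified, and a positive result cannot single it out.

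**A reader might also infer that the aims misattribute the effect.** Aim 1 names the powder as the vehicle, and section 3.6 calls the placebo nutritionally matched. Section 3.6 plans to examine the microbial content of both powders but reports no other compositional difference. A statement that no single-nutrient conclusion will be drawn is enough.

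**Conclusion.** The point holds for the objective in section 3.1, its counterpart in Chapter 1 and the hypothesis in section 2.3. The randomised contrast identifies F + A + FA and nothing finer, at any sample size. A positive result cannot separate synergy from additivity or from one nutrient acting alone. A null gives at most an upper bound on synergy, conditional on non-negative separate effects; at the planned size that bound is about 2.2 CES-D points or 0.2% butyrate if the observed difference is zero.

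This rests on reading synergy as departure from additivity and on the stated contents of the two powders. It does not mean that the design is unsound for its aims, or that further arms are needed: the numbered aims and section 6.2 hypotheses can be addressed as a joint effect with the arms as they are. Whether 20 per group is enough for that joint effect is a separate question and plays no part here.

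**What to change.** 1. In section 3.1 and Chapter 1, replace *synergistic impact* with *combined effect of freeze-dried blueberry powder (a source of fiber and anthocyanins) versus placebo*.
2. In section 2.3, mark the sentence that the nutrients synergistically raise SCFA as mechanistic rationale that this trial does not test. Figure 1 is already labelled as a conceptual model and can stay.
3. In section 6.2, add that the trial will support no conclusion about synergy, or about fiber or anthocyanins alone.

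The cost is a protocol wording change and a narrower claim. No arm, participant, assessment or analysis is added. A factorial trial would be the way to study synergy, but step 5 shows that it is not feasible with 40 participants and belongs to a later study.

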3.2 Overview

This proposal leverages a currently funded individual-level, randomized, double-blind, placebo-controlled, parallel pilot study funded by a National Institute of Aging Roybal Pilot Grant, in 40 sedentary, older adults with depressive symptoms (**IRB Approval Pro00064749; Co-PI [name]**). The primary goal of the parent study is to evaluate the impact of daily dietary fiber and anthocyanin intake on serum inflammatory markers and the engagement of physical activity (via a wrist-worn accelerometer). Recruited participants of the parent trial will be randomized to consume 48 g/day of freeze-dried blueberry powder (a source anthocyanins and dietary fiber) or 48 g/day of a nutritionally matched placebo powder (devoid of anthocyanins and dietary fiber) mixed in water for 12 weeks. As an expansion to the parent study, this ancillary study (**Figure 2**) aims to determine the impact of both dietary fiber and anthocyanins on the gut microbiota, gut-derived metabolites, and depressive symptom severity. Thus, individuals recruited for the parent trial will also be asked to provide a fecal sample for the measures related to the gut microbiota and to answer additional questionnaire-based assessments.

3.3 Inclusion and Exclusion Criteria

The target population of the parent study is sedentary older adults, with minor depressive symptoms. Individuals expressing an interest in participating after recruitment out-reach will be screened in-person (e.g., at HRC or at participant's home). As a part of the parent study, participants will complete several assessments to confirm that they meet the following inclusion criteria.

Inclusion Criteria

- Men and women aged ≥ 65 years
- Self-reporting ≥ 8 hours of sitting per/day (e.g., sedentary behavior)
- Depressive symptoms (defined as ≥ 4 and < 16 points on the center for epidemiological studies depression-scale)

Exclusion criteria have been selected to ensure safety and optimize compliance, while minimizing confounds due to overt disease or conditions that may significantly influence study outcomes. Exclusions may be during the in-person screening as described below:

Exclusion Criteria

- Unwilling to follow the study protocol
- A median daily step count $> 7,500$ steps per day (as measured by the ActiGraph), or per discretion of the PI
- Cognitive impairment (defined as Montreal Cognitive Assessment,³⁷ MoCA < 22 points)
- Self-reporting a history of inflammatory bowel disease/syndrome, major depression, bipolar, schizophrenia, or other psychotic or neurological disorders (e.g., Parkinson's disease), or per discretion of the PI
- Self-reporting type one or type two diabetes
- Allergic to intervention or control products
- Recent use (within the last 3 months) of antibiotics, or per discretion of the PI
- Recent use (within the last 3 months) of probiotics, or per discretion of the PI
- Current substance use disorder (Drug Abuse Screening Test,^{40,41} DAST-10 > 2 points)
- Current alcohol use disorder (Alcohol Use Disorders Identification Test,^{42,43} AUDIT-C ≥ 4 points)
- Unstable anti-depressant use (e.g., change in medication within last 3-6 months), or per discretion of the PI
- Current homicidal or suicidal ideation (assessed via the P4 Suicidality Screener⁴⁴)
- Current psychosis (via the Psychosis and Hallucinations Questionnaire,⁴⁵ PsychHQ > 12 points)
- Manic symptoms (assessed by the Mood Disorder Questionnaire,⁴⁶ MDQ > 5 points)

The majority of subjects that will enroll in this ancillary study will undergo screening as a part of the parent study as outlined in **IRB Pro00064749**. However, if a participant wants to enroll only in this ancillary study, the participant will need to undergo the telephone screening and in-person screening visits as outlined in the parent study (**IRB Pro00064749**).

3.4 Number of Subjects and Study Duration

The parents study aims to recruit a total of 40 individuals (both men and women), in proportion to the gender and racial distribution of the greater Boston population, through local newspaper and internet advertisements, physician referrals, our registry of research volunteers, Hebrew SeniorLife (HSL) senior housing sites, and patient registries (e.g., HRC or Beth Israel Deaconess Medical Center). Participants will remain in the study for a total of 14 weeks.

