4.3 Participant Withdrawal

Any participant who expresses a desire to discontinue participation in the study will be withdrawn at their request immediately. All data collected prior to withdrawal will be maintained in the study data set.

Additionally, a subject may be withdrawn from the study prior to completing all of the study related procedures due to the following conditions:

- Subject safety issues
- Failure of subject to adhere to protocol requirements
- Disease progression
- Subject decision to withdraw from the study (withdrawal of consent)

Withdrawn subjects may not reenter the study unless there are extenuating circumstances (e.g. family emergency or required travel out of town) that interfere with the start of the study before any medications are administered. In this case, they may be scheduled to start over again. If new medical conditions arise or are exacerbated during the study intervention, the withdrawal of a participant will be evaluated by the PI, SO, and/or study psychiatrist.

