6.2 Aim Statistical Methods and Power

Aim 1 Hypothesis: The abundance of microbes that produce SCFA increase after 12 weeks of dietary fiber and anthocyanin supplementation compared to placebo. **Aim 1 Analysis:** To determine taxa and pathways that differ significantly by treatment (blueberry vs. placebo powder), multivariate analyses that accounts for covariates will be carried out using MaAsLin2⁶³ (Multivariate Analysis by Linear Models). MaAsLin2 performs a mixed-effects linear regression of individual log-transformed microbial features (response) on categorical or continuous factors (explanatory variables). A random effects model will be used for repeated measures (i.e., longitudinal data). Linear models will be constructed to assess each feature independently, and adjusted for false discovery using Benjamini-Hochberg FDR. The output of MaAsLin will reveal whether cohort participants with different dietary exposures also differ in relative abundance of a particular bacterial species or pathway in the gut. **Aim 1 Expected Results/Power:** With our proposed sample size of 20/group, we anticipate power 0.95 to detect a 0.314-unit difference in common taxa (~14310 sequences and 0.0954 relative abundance at 5% read usage rate), and a 0.122-unit difference in rare taxa (~2222 sequences and 0.0148 relative abundance at 5% read usage rate) collected at the 2 time points. Approximating as above, the corresponding detection limit for 250 pathways is power 0.95 for a 0.0013-unit difference (1282 sequences at a 33% read usage rate). We assumed we will observe 250 pathways.

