Aim 2 Hypothesis: The fecal SCFA's increase after 12 weeks of dietary fiber and anthocyanin supplementation compared to placebo. **Aim 2 Analysis:** Since butyrate is implicated as the gut-derived metabolite important for depression,³⁰ we will focus on the change in fecal butyrate, but others SCFA and combinations will be explored. Change in fecal butyrate will be calculated between baseline and the final 12 week follow-up. Distribution of change will be summarized using sample quantities and kernel density estimates. We will develop 80% confidence interval estimates of inter- and intra- individual variation (i.e., standard deviation) of change in fecal butyrate, the upper limit will be used to estimate sample size calculations for a subsequent clinical trial. Formal inference and estimation of treatment effects will use a Student's t-test to compare mean change in fecal butyrate in the intervention group compared to placebo. **Aim 2 Expected Results/Power:** A 12 week intervention in non-depressed older adults supplementing usual diet with prebiotic fiber, report mean percent of fecal butyrate concentration increased by 0.4%.⁶⁴ Assuming standard deviation of mean percent change of fecal butyrate = 0.32% and an alpha=0.05, a sample size of 20/group is required to detect a 0.3% change in fecal butyrate.

Aim 3 Hypothesis: Depressive symptom severity (evaluated by CES-D) declines after 12 weeks of dietary fiber and anthocyanin supplementation compared to placebo. **Aim 3 Analysis:** Change in depressive symptom severity (CES-D) will be calculated between baseline and the final 12 week follow-up (we will consider change between baseline and visits at week 4 and 8). The same analyses described for Aim 2, will be implemented for Aim 3. **Aim 3 Expected Results/Power:** Other lifestyle interventions, including dietary strategies, that were designed to reduce depressive symptoms report between a 2-4 point reduction in CES-D scores.⁶⁵⁻⁶⁷ Assuming standard deviation of change of depressive symptoms = 3.5 estimated from other lifestyle interventions and an alpha=0.05, a sample size of 20/group is needed to detect a 2 point reduction in CES-D scores.

CHAPTER 7 DATA MANAGEMENT AND QUALITY

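### The 20 per group stated for Aims 2 and 3 uses the whole recruitment target of 40, so it is reached at week 12 only if nobody is lost

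*Combined protocol and SAP*

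**What the plan says.** **Recruitment.** Section 3.4: "The parents study aims to recruit a total of 40 individuals". Section 3.2 gives the same figure for the parent trial, "in 40 sedentary, older adults with depressive symptoms". No separate target is given for the ancillary study. Section 3.3 (repeated in 5.1) lets a person enrol in the ancillary study alone, without saying how many are expected.

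**Size statements in Section 6.2.**
- Aim 2: "Assuming standard deviation of mean percent change of fecal butyrate = 0.32% and an alpha=0.05", then "a sample size of 20/group is required to detect a 0.3% change in fecal butyrate".
- Aim 3, with an SD of change of 3.5 and alpha 0.05: "a sample size of 20/group is needed to detect a 2 point reduction in CES-D scores".
- Aim 1 is worded differently. It takes the size as given and reports what it can detect: "With our proposed sample size of 20/group, we anticipate power 0.95 to detect a 0.314-unit difference in common taxa".

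**Analysis.** Aim 2 uses a Student's t-test on change in butyrate from baseline to week 12. Aim 3 uses the same analysis on CES-D change and will also consider weeks 4 and 8. Stool is collected only at baseline and week 12 (Section 5.2).

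**Losses.** Section 4.3 foresees that "a subject may be withdrawn from the study prior to completing all of the study related procedures", with non-adherence among the reasons. Section 4.6 lists retention measures, and Section 8.2 says that retention in similar projects has been high, without a figure. No loss rate, inflation factor or replacement rule is given. Section 6.1 specifies intent to treat followed by per protocol, with no method for missing outcomes.

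**The concern.** A sample-size statement for a change-score t-test concerns people who have both measurements. Here that number equals the number to be recruited. As the test is specified, a participant without a week-12 value has no week-12 change and leaves the comparison. The 20 per group is therefore the best case, but Section 6.2 presents it as the number analysed.

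What is at stake is how the results will be read. Power after losses is lower than the size statements imply, and the detectable difference is larger. Sections 6.2 and 8.6 also use this pilot's variation to plan the next trial, so its precision should be described at the number analysed.

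**Working it through.** **Inputs.** From the documents: 40 recruited; 20 per group; alpha 0.05; Aim 2 difference 0.3% and SD 0.32%; Aim 3 difference 2 points and SD 3.5. Assumed, because the documents are silent: a two-sided test, and losses of 10% and 20% spread equally over the groups.

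**1. Allowance for loss.** 2 × 20 = 40, so the allowance is 40 − 40 = 0. If losses are independent, the chance that all 40 complete is 0.95^40 = 13% at 5% loss and 0.90^40 = 1.5% at 10% loss.

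**2. The plan's own sizes.** With standardised difference d = difference/SD, the normal approximation is n per group = 2(z_α + z_β)²/d².
- Aim 2: d = 0.3/0.32 = 0.9375. At 80% power, two-sided, 2(1.960 + 0.842)²/0.9375² = 17.9, so 18 per group, or 19 by the t-distribution. At 90% power, one-sided, the results are 20 and 21. The stated 20 is consistent with either reading; the plan states neither the power nor the sidedness.
- Aim 3: d = 2/3.5 = 0.571. At 80% power, two-sided, 2(1.960 + 0.842)²/0.571² = 48.1, so 49 per group, or 50 by the t-distribution. One-sided, the results are 38 and 39. The stated 20 does not reproduce for the planned two-group test. A one-sample, one-sided test at 80% power gives 20.4.
- Aim 1: not reproducible, because neither a variance nor an alpha is given.

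**3. Power at the number left.** 20 × 0.90 = 18 and 20 × 0.80 = 16. Power is the probability that a noncentral t variable, with 2n − 2 degrees of freedom and noncentrality d√(n/2), exceeds the two-sided 0.05 critical value. For Aim 2 the noncentrality is 0.9375 × √10 = 2.96 at n = 20, 0.9375 × √9 = 2.81 at n = 18 and 0.9375 × √8 = 2.65 at n = 16. For Aim 3 it is 1.81, 1.71 and 1.62.

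| n per group | Aim 2 power | Aim 3 power |
|---|---|---|
| 20 | 82.4% | 42.1% |
| 19 | 80.3% | 40.3% |
| 18 | 78.0% | 38.4% |
| 16 | 72.8% | 34.6% |

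One-sided, Aim 2 power is 90% at 20 per group and still 83% at 16. One-sided Aim 3 power is 55% at 20.

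**4. Difference detectable at 80% power, two-sided.** Detectable d × SD:

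| n per group | d | Aim 2 (× 0.32%) | Aim 3 (× 3.5 points) |
|---|---|---|---|
| 20 | 0.909 | 0.29% | 3.2 |
| 18 | 0.961 | 0.31% | 3.4 |
| 16 | 1.024 | 0.33% | 3.6 |

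**The case against.** The best defence is that this is a 14-week pilot with transport, stipends, reminders and home visits, run by a group that reports high retention. Ancillary-only enrolment could offset some losses. For Aim 2 the margin is not quite zero: 19 per group still gives 80% two-sided, and the hypothesis is directional, so a one-sided test would keep 83% power at 16 per group.

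Much of this stands. It limits the size of the point and means that the loss rates here are illustrations. It does not supply the missing figure: high retention is not complete retention, and no ancillary-only number is given or credited in Section 6.2.

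A reader might infer three stronger things that the documents do not support.
- *That all three aims declare 20 per group a requirement.* Aim 1 only proposes it and reports detectable differences. Its mixed model can retain a participant with one sample, although a baseline-only sample says little about treatment. With no SD or alpha given, its power after losses cannot be derived here.
- *That the stated size will not be reached.* The documents give no loss rate. They support only that it is reached with zero loss, or with additions that they do not quantify.
- *That losses are what weakens Aim 3.* Its stated inputs give about 42% power with everyone retained.

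**Conclusion.** The point holds for Aims 2 and 3: the stated 20 per group equals full recruitment and leaves no allowance for withdrawals that the protocol itself foresees. For Aim 2 the consequence is modest. Two-sided power moves from 82% to 78% or 73% under assumed losses of 10% or 20%, and drops below 80% once more than one person per group is lost. Under a one-sided reading it stays above 80% throughout this range. For Aim 3, which Section 5.4 names as the primary endpoint, loss takes a further 4 to 7 percentage points from a power already near 42%; the mismatch between its inputs and its stated size is the larger and separate problem. For Aim 1 it can be said only that the 0.95 power assumes all 20 per group contribute both samples. This is a minor reporting correction and does not call for a larger pilot.

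**What to change.** Keep recruitment at 40. In Section 6.2:

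- State the number expected to have week-12 data, with the loss rate assumed, and say whether ancillary-only participants are counted.
- State the sidedness and power for Aims 2 and 3.
- Restate the detectable differences at that number, showing 20, 18 and 16 per group. With a two-sided test and 80% power these are 0.29%, 0.31% and 0.33% for Aim 2, and 3.2, 3.4 and 3.6 CES-D points for Aim 3. The Aim 3 sentence should no longer say that 20 per group suffices for 2 points.
- For Aim 1, say that the 0.95 power assumes both samples from all 20 per group, and have it recomputed from its original inputs at the expected evaluable number.

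The cost is a few rewritten sentences with less favourable figures, plus one rerun of the Aim 1 calculation. Enrolment, procedures and the planned tests do not change. Holding 20 evaluable per group by recruiting more would instead take 20/0.90 = 22.2, so 23 per group (46 in total) at 10% loss, or 20/0.80 = 25 per group (50 in total) at 20%. That would still leave Aim 3 far short of the roughly 50 evaluable per group that its 2-point target needs.
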